APPENDIX 5. ADDITIONAL ADVERSE EVENT INVESTIGATIONS

- 1) Adverse Events at the Injection Site
 - Injection site reaction (HLT)
- 2) Hepatic events
 - Drug related hepatic disorders comprehensive search (SMQ, broad and narrow)
- 3) Renal events
 - Acute kidney injury (SMQ, broad and narrow)
- 4) New onset/worsening of diabetes
 - Hyperglycemia/new onset diabetes mellitus (SMQ, narrow)
 - Diabetic Complications (HLGT)
 - Diabetes Mellitus (HLT)
 - Carbohydrate tolerance analyses HLT, excluding PT "Blood glucose decreased"
- 5) Hypersensitivity
 - Hypersensitivity' (SMQ, broad and narrow) excluding
 - PTs 'infusion site %' ('infusion site dermatitis', 'infusion site eczema', 'infusion site hypersensitivity', 'infusion site rash', 'infusion site urticaria', 'infusion site vasculitis) and
 - PTs 'injection site %' ('injection site dermatitis', 'injection site eczema', 'injection site hypersensitivity', 'injection site rash', 'injection site urticaria' and 'injection site vasculitis')
- 6) Neurological events and neurocognitive disorders

Neurological events

- Demyelination, (SMQ, broad and narrow)
- Peripheral neuropathy, (SMQ, broad and narrow)

Neurocognitive disorders

- Deliria (including confusion), (HLGT)
- Cognitive and attention disorders and disturbances, (HLGT)

• Dementia and amnestic conditions, (HLGT)

- Disturbances in thinking and perception (HLGT)
- Mental impairment disorders (HLGT)

7) Ophthalmologic events

- Optic nerve disorders, (SMQ, broad and narrow)
- Retinal disorders, (SMQ, narrow)
- Corneal disorders, (SMQ, narrow)
- 8) Major cardiovascular events (MACE)

Cardiac death

- Fatal SAEs in Cardiac disorders SOC
- Fatal SAEs in General disorder SOC: PTs 'Death', 'Sudden cardiac death', 'Cardiac death', 'Apparent death'

Cardiac arrest

• PT 'Cardiac arrest'

Non-fatal MI

• Myocardial infarction (SMQ, broad and narrow), nonfatal events only

Stroke

• Central Nervous System hemorrhages and cerebrovascular accidents (HLT), fatal and non-fatal events

APPENDIX 6. CLINICALLY RELEVANT ADVERSE EVENTS AT THE INJECTION SITE PREFERRED TERMS

Injection site atrophy
Injection site cellulitis
Injection site dermatitis
Injection site eczema
Injection site erythema
Injection site fibrosis
Injection site granuloma
Injection site hypersensitivity
Injection site infection
Injection site inflammation
Injection site ischaemia
Injection site lymphadenopathy
Injection site necrosis
Injection site nerve damage
Injection site photosensitivity reaction
Injection site pruritus
Injection site pustule
Injection site rash
Injection site reaction
Injection site recall reaction
Injection site scar
Injection site thrombosis
Injection site ulcer
Injection site urticaria
Injection site vasculitis
Injection site vesicles

STATISTICAL ANALYSIS PLAN ADDENDUM

Protocol No.: MDCO-PCS-17-03 (ORION-9)

A PLACEBO-CONTROLLED, DOUBLE-BLIND, RANDOMIZED TRIAL TO EVALUATE THE EFFECT OF 300 MG OF INCLISIRAN SODIUM GIVEN AS SUBCUTANEOUS INJECTIONS IN SUBJECTS WITH HETEROZYGOUS FAMILIAL HYPERCHOLESTEROLEMIA (HeFH) AND ELEVATED LOW-DENSITY LIPOPROTEIN CHOLESTEROL (LDL-C)

U.S. IND NO.: 127,589 EudraCT No.: 2017-002472-30 PROTOCOL VERSION: GLOBAL AMENDMENT #4 SAP VERSION: v3.0 13 Sep 2019

TABLE OF CONTENTS

1.	INTRODUCTION	2
2.	CHANGES TO ANALYSES	5
2.1.	Concomitant Medications	5
2.2.	Subgroups	5
2.3.	Laboratory Tests	5
2.4.	Statin/LMT Use at Baseline.	5
2.5.	Appendix 2: Multiple Imputation Washout Model	4

1. INTRODUCTION

The following Statistical Analysis Plan Addendum summarizes changes to the SAP that were requested by the FDA after the SAP was finalized, the database was locked, and the study was unblinded. An update to the effects used in the imputation model and a clarification of the steps used for the multiple imputation washout model found in Appendix 2 of the SAP are also included.

2. CHANGES TO ANALYSES

2.1. Concomitant Medications

The statin intensity (low, moderate, high) will be defined by clinical review of the data according to American College of Cardiology/American Heart Association (ACC/AHA) classification of high intensity and based on the specific statin drug name, dose (unit), and frequency recorded in the data. Two types of summaries will be presented for the analysis of statins. For the first summary, simvastatin 40 mg will be included in the high intensity group (as originally presented in the SAP). For the second summary, simvastatin 40 mg will be included in the moderate intensity group based on the FDA feedback received on September 13, 2019.

2.2. Subgroups

Select baseline, efficacy, and safety variables will be summarized by subgroup. One of the subgroups will be baseline statin intensity. For this subgroup classification, simvastatin 40 mg will be considered as moderate intensity.

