3. STUDY DESIGN

3.1. Type/Design of Study

This study will be a Phase III, placebo-controlled, double-blind, randomized study in 400 subjects with HeFH and elevated LDL-C despite maximum tolerated dose of LDL-C lowering therapies to evaluate the efficacy, safety, and tolerability of subcutaneous inclisiran injection(s). The study will be a multicenter, international study. Informed consent will be obtained from subjects before the initiation of any study-specific procedures.

[figure not shown]
Subjects will be screened and approximately 400 eligible subjects will be randomized: 200 subjects will be randomized to inclisiran sodium 300 mg and 200 subjects randomized to placebo. Due to faster than expected enrollment, actual enrollment was 482 subjects.

Treatment allocation will be stratified by country and by current use of statins or other lipid-modifying therapies. Enrollment of statin intolerant subjects will be capped at 15% of total study enrollment. Each subject will receive an injection on Day 1 of blinded inclisiran or placebo, a second injection on Day 90 and subsequent injections on Day 270 and Day 450.

Subjects who have completed the study to Day 540 will be given the opportunity to enroll in a separate long-term extension study to collect long-term efficacy and safety data.

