6.4.5. Concomitant Medications

Summaries of each prior (pre-baseline, defined as medication stopped 1 day before first dose date of study medication) medication and concomitant (Day 1 or later, any medications started or continued after study medication on Day 1 are considered as Day 1 concomitant medication) medications will be provided by treatment group for ITT, FAS, mITT, and safety population. Additional summaries will be provided for lipid modifying therapy use. Medications will be coded using the World Health Organization (WHO) drug dictionary (B3 WHO DDE+HD Sep 2017). Subjects will be counted only once within each period by medication.

The statin intensity (low, moderate, high) will be defined by clinical review of the data according to American College of Cardiology/American Heart Association (ACC/AHA) classification of high intensity and based on the specific statin drug name, dose (unit), and frequency recorded in the data. The high intensity group will include simvastatin 40 mg. A shift table for lipid modifying therapy statin intensity from baseline to Day 540 (EOS) will also be provided. The statin intensity of the last statin taken on or prior to Day 540 (EOS) will be used for the post-baseline statin.

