6.4.7. Subgroup Analysis

Analysis of efficacy and safety will also be performed for subgroups of interest including:

Table 3: Subgroups for Analysis

Table # [1]		Categories and comm	nents		
1	Gender	Male	Female		
2	Age #1	$< 65 \text{ vs} \ge 65 \text{ years}$			
3	Age #2	$< 75 \text{ vs} \ge 75 \text{ years}$			
4	Body mass index #1	≤ vs > median			
5	Body mass index #2	Quartiles			
6	Race	White	Black	Other	
7	Baseline statin use	Yes	No		
8	Baseline statin intensity	High intensity	Not high intensity		
9	Other lipid management therapy	Any statin with other lipid management therapy	No statin but other lipid management therapy	No lipid management therapy	
10	Baseline triglyceride level #1	<200 mg/dL vs ≥200 mg/dL			
11	Baseline triglyceride level #2	≤ vs > median			
12	Metabolic disease [2]	Diabetes	Metabolic syndrome without diabetes	Neither	
13	ASCVD status [3]	ASCVD	ASCVD risk equivalents		
14	Renal impairment by eGFR categories - mL/min/1.73m ² [4]	≥15 to <30	≥30 to <60	≥60 to <90	≥90
15	History of allergy [5]	Yes	No		
16	Baseline LDL-C #1	≤ vs > median			
17	Baseline LDL-C #2	Quartiles			
18	Study center region	North America	Europe	South Africa	
19	Post baseline LDL-C [6]	<pre><25 at any time point vs >25 mg/dL at all time points</pre>			
20	Phenotype [7]	FH	Non-FH		
21	Baseline ezetimibe use	Yes	No		

- [1] Numbers provide the order that the subgroups will be presented.
- [2] Metabolic syndrome is not based on medical history but will be defined according to the American Heart Association (AHA) definition (see Reference 1).
- [3] Derived from the targeted medical history page: CHD=Yes or CVD=Yes or PAD=Yes then the subject is ASCVD; all other subjects are ASCVD risk equivalent
- [4] Creatinine clearance (CrCl) values using the Cockroft and Gault estimation:
- $CrCl = \{((140-age) \times weight)/(72xSerum Creatinine)\} \times 0.85 \text{ (if female)}$
- [5] A history of allergy was identified using the following high-level group term (HLGT): allergic conditions.
- [6] For descriptive summary of PCSK9 data only.
- [7] Phenotype is defined using Simon Broome diagnostic criteria (see Appendix A in protocol). Definite Familial Hypercholesterolemia (FH) and Possible Familial Hypercholesterolemia will be included as FH.

Baseline variables to be analyzed by subgroup:

Disposition	
Protocol Deviations	

Demographics and Baseline Characteristics
Targeted Medical History
Other Medical History
Medical History of Partial or Complete Statin Intolerance

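### The statin-intensity subgroup was redefined after unblinding and is listed only in its new form, and Table 3 does not say where subjects on no statin belong

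*SAP*

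**What the plan says.** SAP 6.4.5 grades statin use as low, moderate or high from the drug, dose and frequency recorded, and settles one case by name: "The high intensity group will include simvastatin 40 mg". SAP 6.4.7, Table 3 row 8, then uses two levels for the baseline statin intensity subgroup, High and "Not high intensity". Both co-primary endpoints and the key secondary endpoints are to be analysed by subgroup.

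The SAP Addendum says in its introduction that its changes were "requested by the FDA after the SAP was finalized, the database was locked, and the study was unblinded". Addendum 2.1 covers the concomitant-medication tables: "Two types of summaries will be presented for the analysis of statins". Of these, "For the first summary, simvastatin 40 mg will be included in the high intensity group", and the second puts that dose in the moderate group, citing FDA feedback of 13 September 2019. For the subgroup, Addendum 2.2 gives one rule only: "For this subgroup classification, simvastatin 40 mg will be considered as moderate intensity".

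Subjects on no statin are eligible under Protocol Appendix B if complete statin intolerance is documented. Protocol 3.1 limits their number indirectly: "Enrollment of statin intolerant subjects will be capped at 15% of total study enrollment".

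**The concern.** There are two separate issues.

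First, a subgroup definition was changed when the data were already unblinded, and the version fixed beforehand is not listed for output. Whatever the reason for the change, a reader who sees a difference, or none, between the row 8 groups has no means of telling whether the pre-specified split would have shown the same. Protocol Appendix B accepts simvastatin 40 mg as a qualifying background dose, so the subjects who move need not be few.

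Second, row 8 is a two-way split of a scale that has no level for subjects on no statin. If they are counted in Not high, a contrast labelled intensity is partly a contrast of statin use with non-use. This gap was in Table 3 before the addendum.

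What is at stake is the reading of one subgroup row, not the trial's conclusion.

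**Working it through.** The plan gives no sample size, power or count for this subgroup, so there is no figure of its own to reproduce.

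**Step 1. How the addendum treats each original analysis.**

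| Item | Original | Addendum | Original kept? |
|---|---|---|---|
| Statin summaries | SAP 6.4.5: simvastatin 40 mg high | 2.1: adds a moderate version | Yes |
| Hy's Law table | SAP 6.4.8.2: normal baseline required | 2.3: adds a version ignoring baseline | Yes |
| Statin-intensity subgroup | SAP 6.4.7 row 8, read with 6.4.5 | 2.2: moderate | Not listed |

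Of these three FDA-driven changes, only the subgroup lacks a parallel original.

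**Step 2. What the reclassification can do.** Let n0 be subjects on no statin (if placed in Not high), m those on other low or moderate statins, and s those on simvastatin 40 mg. Not high grows from n0 + m to n0 + m + s. With w = s/(n0 + m + s), the treatment effect in Not high shifts by about w × (effect in simvastatin 40 mg users − effect in the old Not high group). The documents give neither w nor the gap.

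The only bound they offer is on n0: 0.15 × 482 = 72.3, so at most 72. That holds if the cap was respected and every subject on no statin counts as statin intolerant. For the rest I assume ranges: n0 = 10, 36 or 72; m = 24, 72 or 120; s = 10, 24 or 48.

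- Simvastatin 40 mg share of the new Not high group: from 10/(72 + 120 + 10) = 5% to 48/(10 + 24 + 48) = 59%.
- No-statin share before the addendum: from 10/130 = 8% to 72/96 = 75%.
- No-statin share after it: from 10/178 = 6% to 72/106 = 68%.

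The no-statin share falls in every combination, because the denominator grows and the numerator does not. The addendum therefore dilutes the mixing with non-users; it does not cause it.

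**Step 3. Precision of the contrast.** With 1:1 allocation in each subgroup, SE = SD × √(4/n1 + 4/n2). I take SD = 20, the planning value in mg/dL from SAP 6.1, and assume it also serves for percentage points.

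- Not high 50, High 432: 20 × √(4/50 + 4/432) = 6.0.
- Not high 120, High 362: 20 × √(4/120 + 4/362) = 4.2.
- Not high 200, High 282: 20 × √(4/200 + 4/282) = 3.7.

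The difference detectable with 80% power at two-sided 0.05 is 2.80 × SE, about 17 at the first size and 10 at the last. The contrast is imprecise but estimable.

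**Step 4. What other rows recover.** Row 7 (statin yes/no) and two categories of row 9 report subjects on no statin separately. Row 7 Yes pools high with moderate and low users, so together with row 8 High and the group sizes it gives a rough moderate-or-low effect, without an interval. Neither row identifies simvastatin 40 mg users. The two summaries in Addendum 2.1 would show how many subjects move, but not their LDL-C results.

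**The case against.** The strongest reply is that the change came from the regulator, is a fixed rule on a baseline drug and dose, and touches a subgroup outside the type I error hierarchy, for which no interaction test is specified. All of that stands. Nothing in the documents suggests that the sponsor chose the new cut after seeing results, and a reader should not infer it from the timing. But a request for the moderate version explains adding it. The documents do not say that the original should go.

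Addendum 2.2 also does not expressly withdraw the earlier version; its absence is read from silence. That is fair, but 2.1 states in terms that two versions will be shown, so a programmer working from 2.2 would most likely produce one.

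On subjects with no statin, the reply is that intensity is derived from a drug, dose and frequency, so someone with none of these may simply be unclassified. That reading is as natural as the literal one. It leaves the need for a sentence in the plan.

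A reader might go further and infer that row 8 cannot show any dependence on statin intensity. The documents do not support this: the contrast can be estimated, and rows 7 and 9 allow a partial check. Nor do they support a figure for the confounding. Assuming 24 to 72 non-users among 120 Not high subjects, and a 6-point gap in effect between non-users and users, gives 24/120 × 6 = 1.2 to 72/120 × 6 = 3.6 points. Apart from the ceiling of 72 these inputs are assumed, the result is below one standard error (4.2), and it does not measure the reclassification.

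**Conclusion.** The point holds as a minor one about reporting. The text is clear that the pre-specified class of simvastatin 40 mg was high, that the addendum came after unblinding, and that 2.2 lists only the moderate version while 2.1 and 2.3 keep their originals. It follows that readers of row 8 cannot check whether the pattern depends on the reclassification.

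The placement of subjects on no statin is an open ambiguity in Table 3, not a stated error, and the addendum did not create it. If they are in Not high, intensity is confounded with statin use to an unknown degree.

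No size can be given for either effect. The shares in the working show only that both could be anything from slight to substantial under assumed counts. I take no position on which class is right for simvastatin 40 mg.

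**What to change.** In Addendum 2.2:

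- Report the row 8 efficacy results twice: with simvastatin 40 mg as high (labelled pre-specified) and as moderate (labelled FDA-requested, post-unblinding).
- State where subjects on no statin go, by restricting row 8 to statin users or by showing them as their own level.
- SAP 6.4.7 lists the statin-intensity shift table among the variables run by subgroup, while Addendum 2.2 speaks only of selected variables. If that table is run by row 8, pair each version with the matching classification. Otherwise subjects graded high at baseline would appear inside Not high.

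The data are already classified both ways for Addendum 2.1, so the work is a few more table rows. The drawback is smaller categories with wider intervals, in a contrast that is already imprecise.

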2.3. Laboratory Tests

The number and percentage of subjects satisfying Hy's Law will also be tabulated by treatment group based on the following lab findings:

- Any elevated post-baseline aminotransferases defined as:
 - $ALT > 3 \times ULN \text{ or }$
 - AST $> 3 \times ULN$
- Elevated post-baseline serum total bilirubin (TBL) > 2 x ULN and serum alkaline phosphatase (ALP) levels < 2 x ULN

Subjects must meet all of the criteria listed above at the same time point and have normal lab parameters (ALT, AST, TBL) at baseline to be considered a Hy's Law case. Per FDA feedback, a second summary will be presented that includes all subjects who meet all of the criteria listed above at the same time point without regard to the baseline lab parameter (ALT, AST, TBL) results.

2.4. Statin/LMT Use at Baseline

The small number of subjects who were not currently using statins or other lipid-modifying therapies (LMT) at baseline caused convergence issues with the imputation models. As such, the statin/LMT use at baseline effect was removed from the multiple imputation washout model and Control Based - Pattern Mixture Model imputation steps. Note that the statin/LMT use at baseline effects were already removed from the analysis models.

2.5. Appendix 2: Multiple Imputation Washout Model

Minor changes were made to the description of the multiple imputation washout model to aid in the understanding of the method. The changes did not alter the way the method was implemented. The final wording is provided below.

A multiple imputation washout model will be utilized for the primary efficacy analysis of the percentage change in LDL-C from baseline to Day 510 endpoint. The washout model can be thought of as a modified control-based Pattern-Mixture Model (PMM) that will be used to explore the possibility of data missing not at random (MNAR) for subjects who discontinued the study early. For subjects who discontinued the study early, their missing values will be imputed under the assumption that their outcome would be similar to those in the placebo group with similar background characteristics. For subjects in the inclisiran group only missing Day 510 values will be imputed. For subjects in the placebo group their missing values over all visits after early termination will be imputed based on the missing at random (MAR) assumption. Multiple imputation will be used to account for uncertainty in the imputation process and results from the imputed datasets will be combined using Rubin's method. Further details are provided below.

Windowing will be performed first (see Section 6.3.3) and any missing data will be imputed using the following steps.

For the placebo group the following variables will be included in a multiple imputation procedure (SAS PROC MI), this assumes missing data are MAR:

- Baseline value of efficacy measurement (continuous)
- Observed value of efficacy measurement at Day 90 (continuous)
- Observed value of efficacy measurement at Day 150 (continuous)
- Observed value of efficacy measurement at Day 270 (continuous)
- Observed value of efficacy measurement at Day 330 (continuous)
- Observed value of efficacy measurement at Day 450 (continuous)
- Observed value of efficacy measurement at Day 510 (continuous)
- Observed value of efficacy measurement at Day 540 (continuous)

For the subjects in the inclisiran group who completed all 4 doses and have data present at Day 540 (considered to have completed the study) the following variables will be included in a multiple imputation procedure (SAS PROC MI), this assumes missing data are MAR:

- Baseline value of efficacy measurement (continuous)
- Observed value of efficacy measurement at Day 510 from the inclisiran group (continuous)

For the remaining subjects in the inclisiran group the following variables will be included in a multiple imputation procedure (SAS PROC MI), this assumes missing data are MNAR:

- Baseline value of efficacy measurement (continuous)
- Observed value of efficacy measurement at Day 510 from the placebo group (continuous)
- 1. Intermittent missing data in the placebo treatment group will be imputed using MCMC methods, assuming MAR. SAS PROC MI will be utilized for this step using the MCMC impute=monotone option. A total of 100 datasets will be created. These datasets will be utilized in Step #2.

- 2. The remaining missing values in the placebo group with a monotone missing data pattern will be imputed in this step. Missing data will be imputed assuming data are MAR. Only subjects in the placebo group will be utilized in this step. SAS PROC MI will be used to impute missing values utilizing the monotone reg option. This will be performed for the 100 datasets. After this step, the 100 datasets will be fully imputed for the placebo treatment group. These datasets will be utilized in Step #4.
- 3. Subjects in the inclisiran group who received all 4 doses of study medication, have the Day 510 value missing, and have evaluable data at Day 540 will be included in this step. Missing values at Day 510 will be imputed assuming data are MAR. Only subjects in the inclisiran group will be included in this step. Observed Baseline and Day 510 data will be utilized to impute missing Day 510 data utilizing SAS PROC MI. This will be performed 100 times to create 100 datasets that are fully imputed at Day 510.
- 4. The remaining missing values at Day 510 in the inclisiran group will be imputed in this step. Note that the subjects with imputed inclisiran Day 510 data from Step #3 will not be utilized in this step. Control-based PMM imputation will be performed. With this imputation model, the missing efficacy measurements in the inclisiran group will not be constructed from the observed data in the inclisiran group but rather from the observed and imputed data in the placebo group at Day 510. Baseline data will also be utilized in the imputation. The MNAR statement in SAS PROC MI will be used to impute missing values. This will be performed for the 100 datasets.
- 5. The imputed data from Step #3 will be combined with the imputed data from Step #4 to create 100 fully imputed datasets.
- 6. A total of 100 fully imputed datasets will be created (M=100). Since multiple imputation is a stochastic method, slight differences in output can be expected for different initial states of the random number generator. The seed numbers will be identified in the SAS programs to allow for reproducibility.
- 7. After the missing data imputation is completed using the above steps, absolute change/percentage change values will be calculated in each of the imputed datasets at each visit.
- 8. These 100 datasets will be analyzed using ANCOVA models with fixed effect of treatment group and baseline LDL-C as a covariate for the percent change of LDL-C from baseline to Day 510 primary efficacy endpoint.
- 9. Treatment effects (difference in LS means between treatments) from these 100 analyses will then be combined using Rubin's Method via SAS PROC MIANALYZE procedure for each endpoint.
